#### **Amendment 8**

**Issue date: 24-JUL-2019**

##### **Summary of Changes:**

1. Section 5.1 Inclusion criteria 5. The following change was made (changes in bold):

Lymphocyte count	>800 ≥ 400 cells/μL. (See Section 3.3 for instructions for blood draws for PBMC collection.)
------------------	--

2. Section 3.2 (Study Flowchart). Footnote L was added.
3. Section 3.3 (Additional Instructions for Blood Draws for PBMC Collection) was added.

##### **Rationale for the changes:**

The original lymphocyte requirement of 800 cells/μL was intended to allow for enough PBMCs to be collected for correlative analyses. However, the requirement was not allowing otherwise qualified subjects to enroll in the study. As the restriction was intended only to optimize the PBMC collection, it was decided to lower the lymphocyte requirement to 400 cells/μL with adjustment to blood volume collection for PBMCs when appropriate for the particular subject (See Laboratory Manual for additional details on blood volume and weight restriction).

#### **Amendment 8.1**

**Issue date: 17-SEP-2019**

##### **Rationale for the changes:**

The decision was made not to enroll any subjects into the Control Group for Arms A and B. As the protocol was previously amended to allow subjects pretreated with PD-1/PD-L1 inhibitors, baseline correlative sample testing can serve the purposes of the Control Group. In addition, reported results of the Phase III MYSTIC, ARCTIC and NEPTUNE studies of durvalumab plus tremelimumab in NSCLC did not find the combination to be superior to standard of care chemotherapy making it inappropriate to recruit subjects to the control treatment arm with tremelimumab and/or durvalumab without vaccine.

##### **Summary of Changes:**

All references to the Control Group for Arms A and B were removed. The following sections were affected:

- Synopsis
- Section 3.1 (Study Design)
- Section 3.1.2 (Enrollment Randomization), including Figure 1 (Enrollment Schema)
- Section 3.1.6 (Sample Size Considerations)
- Section 3.1.7 (Treatment Arms and Treatment Schema)
- Section 3.1.7.2 (Dose Expansion Phase)

CONFIDENTIAL

- Section 3.2 (Study Flowchart).
  - Removed footnote “I” which referenced the Control Group for Arm A/Arm B.
  - Footnote “L” (“See Section 3.3 for instructions for blood draws for PBMC collection”) was repositioned as Footnote “i”. Note: Footnote L was added per Amendment 8.
- Section 4.3.1.2.1 (Immune Monitoring for Responses to BI 1361849 Vaccine). The last 2 sentences in the first paragraph were deleted as they referred to the Control Group.
- Section 4.3.2 (Subject Evaluation and Statistics). The last bullet was changed as follows:  
~~The analysis of antigen-specific cell-mediated immune response by ICS is required to include all BI®1361849 antigens and including negative controls baseline values to be fully evaluable.~~ ¶

#### **Amendment 9 (27-AUG-2020)**

**NOTE: Amendment 9 was not released. Further clarifications were added and all changes were incorporated into Amendment 9.1.**

#### **Amendment 9.1**

**Issue date: 01-SEP-2020.**

1. Section 4.3.1.2 (Biological Activity in Blood Samples): Based on the decision of CureVac/Boehringer Ingelheim to discontinue immune monitoring testing, the collection of blood samples for this purpose was also discontinued. A note was added to Section 4.3.1.2 to indicate that the following sample collections were discontinued:
  - Blood for PaxGene RNA and DNA
  - Blood (PBMC and plasma) for flow cytometry and biological assays
  - Blood for humoral responses and other biomarkers
 Blood collections for exosomal profiling and tumor biopsy collections were continued.
2. ctDNA testing was removed from Section 4.3.1.2 .
3. Section 3.2 (Study Flowchart).
  - Notes were added to indicate discontinued blood collection for PaxGene RNA/DNA, PBMC, and humoral responses
  - Notes were added to footnotes i, J, and k to indicate the discontinuation of blood collection for PaxGene RNA/DNA, PBMC, and humoral responses
  - Note was added to footnote J to indicate that Visits 6, 14, and 28 would no longer be required per Amendment 9.1
  - ctDNA was deleted from the blood for exosomal profiling collection
4. References to the Note in Section 4.3.1.2 were also added to Section 3.3 (Additional Instructions for Blood Draws for PBMC Collection), Section 4.3.1 (Endpoints and Assessment Methods); Section 4.3.1.2.1 (Immune Monitoring for Responses to BI 1361849 Vaccine), and Section 4.3.2 (Subject Evaluation and Statistics).
5. Section 5.1 (Inclusion Criteria): The following note was added to criterion #2 for clarification:  
 NOTE: Per Amendment 9.1, biopsies should not be taken from a target lesion unless that is the only suitable lesion, in which case it should be of reasonable size.

CONFIDENTIAL

The same note was added to Section 4.3.1.1 (Tumor Microenvironment) for item #1 and to Section 3.2 (Flowchart), footnote g, item #1.

**Amendment 10.0**

**Issue date: 30-JUL-2021.**

the following changes were made to the protocol:

1. All post study follow-up will be discontinued as of 31 October 2021. The following note was added to Sections 3.1.15 (Duration of Study), 3.1.16 (On Study and Post Study Follow-up), and 4.2.1 (Efficacy Endpoints and Assessment Methods):  
“NOTE: Per Amendment 10.0, all post study follow-up will be discontinued as of 31 October 2021.”
2. Section 4.3.1 (Biological Activity Endpoints and Assessment Methods) and Section 4.3.2 (Subject Evaluation and Statistics). The following note was added: “NOTE: Per Amendment 10.0, all correlative testing will be discontinued, with the possible exception of PD-L1 expression and whole exome sequencing.”
3. Section 3.2 (Flowchart). Footnote “L” was added: “Per Amendment 10, Post Study Follow-up will be discontinued as of 31 October 2021; and all correlative testing will be discontinued, with the possible exception of PD-L1 expression and whole exome sequencing.”
4. In addition to the above changes, AstraZeneca provided updated language for Section 7.1.2 (Additional reporting requirements for this study). Section 7.1.2.4 (New Cancers) and Section 7.1.2.5 (Deaths) were added.

CONFIDENTIAL

### 8.3 Dose Adjustments and Delays for Durvalumab and Tremelimumab

If a toxicity occurs that requires toxicity management in accordance with Sections 8.3 or 8.4, and the toxicity causing drug can be clearly identified, then the respective guideline should be followed. If the toxicity causing drug cannot be identified, then the more conservative guideline should be followed.

#### 8.3.1 Durvalumab and Tremelimumab Dose Modification Due to Toxicity

Durvalumab (MEDI4736) and tremelimumab administration may be modified or discontinued as a result of toxicities as described in the table below.

Additional information and guidance regarding dose modification due to toxicity are provided from Medimmune in the following guidelines:

***“Medimmune’s Dosing Modification and Toxicity Management Guidelines for Immune-mediated, Infusion Related, and Non Immune-mediated Reactions (MEDI4736 (durvalumab) Monotherapy or Combination therapy with Tremelimumab or Tremelimumab monotherapy).”***

Dose modifications will not be required for AEs that are clearly not attributed to durvalumab or tremelimumab (such as an accident) or for laboratory abnormalities that are not deemed to be clinically significant.

MEDI4736 (M) and Tremelimumab (T) Dose Modification Due to Toxicity
Note: If M and T dosing is held temporarily until resolution of the event as per instructions below, treatment should resume at the next scheduled treatment date.
Immune-related Adverse Events (irAEs) Immune-related adverse events are defined as AEs of immune nature (i.e., inflammatory) in the absence of a clear alternative etiology. Maximum supportive care, including immunosuppressive medications, such as high dose steroids, is allowed to induce resolution of the event. However, infliximab should not be used for management of immune-related hepatitis. In addition to the criteria for permanent discontinuation of M and T depicted below, permanently discontinue M and T also for: 

• Any Grade rash with bullous skin formations.

• Inability to reduce corticosteroid to a dose of <math>\leq 10</math> mg of prednisone per day (or equivalent) within 12 weeks after last dose of study drug/regimen.

• Recurrence of a previously experienced Grade 3 treatment-related AE following resumption of dosing.

• Any Grade biopsy-proven immune-mediated myocarditis.

 Grade 1 

• In general, no dose modification required.

• For pneumonitis/interstitial lung disease and myocarditis, consider holding M and T dosing as clinically appropriate and during diagnostic work-up for other etiologies.

CONFIDENTIAL

## Grade 2

- In general, hold M and T until resolution to  $\leq$  Grade 1 and after the end of any steroid taper, and discontinue M and T permanently if such resolution does not occur within 60 days (30 days for neurotoxicities). Criteria for temporary hold or permanent discontinuation of M and T may differ by event as detailed below.
- For *myositis/polymyositis*, hold M and T until resolution to  $\leq$  Grade 1; permanently discontinue M and T if it does not resolve to  $\leq$  Grade 1 within 30 days or if there are signs of respiratory insufficiency.
- For *pneumonitis/interstitial lung disease and myocarditis*, the decision to reinitiate M and T upon resolution shall be based upon treating physician's clinical judgment (as long as the event does not meet DLT criteria).
- For *peripheral neuromotor syndromes*, such as *Guillain-Barre* and *Myasthenia Gravis*, follow general instructions above, but always discontinue M and T permanently if there are signs of respiratory insufficiency or autonomic instability.
- For *endocrinopathies, other than isolated hypothyroidism and isolated Type 1 diabetes mellitus*, follow general instructions above, but subjects may be retreated if the endocrinopathy is controlled and the subject is clinically stable while requiring steroid doses of  $\leq$  10 mg/day prednisone equivalent.
- For *isolated hypothyroidism* managed with hormone replacement therapy, *isolated Type 1 diabetes mellitus* treated with appropriate diabetic therapy, and for *sensory neuropathy/neuropathic pain*, holding M and T is at the discretion of the Investigator.
- For *elevated creatinine* or *rash*, M and T should be held until resolution to  $\leq$  Grade 1 or baseline and after completion of steroid taper.
- For *vitiligo*, no dose modification required.

## Grade 3

- In general, hold M and T until resolution to  $\leq$  Grade 1, and after the end of any steroid taper, and discontinue M and T permanently if such resolution does not occur within 60 days (30 days for neurotoxicities and rash). Criteria for permanent discontinuation of M and T may differ by event as detailed below.
- For *myositis/polymyositis*, follow Grade 2 instructions above.
- For *peripheral neuromotor syndromes* (such as *Guillain-Barre* and *Myasthenia Gravis*), apply respective Grade 2 rules.
- For *endocrinopathies*, follow Grade 2 instructions above.
- For *diarrhea/colitis*, permanently discontinue M and T if toxicity does not improve to  $\leq$  Grade 1 within 14 days.
- For *pneumonitis/interstitial lung disease, myocarditis, and elevated serum creatinine (e.g., nephritis or renal dysfunction)*, always discontinue M and T permanently.
- For *asymptomatic increases of amylase or lipase* levels, hold M and T, and if complete work up shows no evidence of pancreatitis, M and T may be continued.
- For *hepatitis*, discontinue M and T permanently for (1) transaminases or bilirubin not resolving to  $\leq$  Grade 1 or baseline within 14 days, (2) transaminases  $> 8 \times$  the upper limit of normal (ULN) or bilirubin  $> 5 \times$  ULN, or (3) any case meeting Hy's law criteria (as defined in FDA Guidance Document "Drug-Induced Liver Injury").
- For *rash*, M and T should be held until resolution to  $\leq$  Grade 1 or baseline.

CONFIDENTIAL

MEDI4736 (M) and Tremelimumab (T) Dose Modification Due to Toxicity

Grade 4
 
 
• In general, discontinue M and T permanently.
 
• For endocrinopathies, follow Grade 2 instructions above.
 
• For asymptomatic increases of amylase or lipase levels, hold M and T, and if complete work up shows no evidence of pancreatitis, M and T may be continued.
 

Infusion-related Reactions
 
Grade 1
 
 
• The infusion rate of M and T may be decreased 50% or temporarily interrupted until resolution of the event.
 
• Acetaminophen and/or antihistamines may be administered per institutional standards at the discretion of the Investigator.
 
• Premedication for subsequent doses should be considered.
 
• Steroids should not be used for routine premedication of <math>\leq</math>Grade 2 infusion reactions
 
 
Grade 2:
 
 
• Same as Grade 1, but consider giving subsequent infusions at 50% of the initial infusion rate.
 
 
Grade 3 and 4:
 
 
• The infusion must be stopped immediately and treatment permanently discontinued.
 
• Manage severe infusion-related reactions per institutional standards (e.g., IM epinephrine, followed by IV diphenhydramine and ranitidine, and IV glucocorticoid).
 


All other Adverse Events
 
Grade 1
 
 
• No dose modification required.
 
 
Grade 2
 
 
• Hold M and T until resolution to <math>\leq</math> Grade 1 or baseline, and discontinue M and T permanently if such resolution does not occur within 60 days.
 
 
Grade 3
 
 
• Hold M and T. If AEs downgrade to <math>\leq</math> Grade 2 within 7 days or resolve to <math>\leq</math> Grade 1 or baseline within 14 days, resume M and T administration at next scheduled dose. Otherwise, discontinue M and T permanently.
 
 
Grade 4
 
 
• In general, discontinue M and T permanently.
 
• For isolated lab results, decision to discontinue should be based on accompanying clinical signs/symptoms and per Investigator's clinical judgment and in consultation with the Sponsor.
 

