#### **7.1.2.3 Hepatic Function Abnormality**

Hepatic function abnormality (as defined in Section 7.1.8 in a study subject, with or without associated clinical manifestations, is required to be reported as "hepatic function abnormal" **within 24 hours of knowledge of the event** to the Sponsor, unless a definitive underlying diagnosis for the abnormality (e.g., cholelithiasis or bile duct obstruction) that is unrelated to investigational product has been confirmed.

- If the definitive underlying diagnosis for the abnormality has been established and is unrelated to investigational product, the decision to continue dosing of the study subject will be based on the clinical judgment of the investigator.
- If no definitive underlying diagnosis for the abnormality is established, dosing of the study subject must be interrupted immediately. Follow-up investigations and inquiries must be initiated by the investigational site without delay.

Each reported event of hepatic function abnormality will be followed by the Investigator and evaluated by the Sponsor and MedImmune/AstraZeneca.

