Increased transaminases have been reported during treatment with anti-PD-L1/anti-PD-1 antibodies (see IB). Inflammatory hepatitis has been reported in 3% to 9% of subjects treated with anti-CTLA-4 monoclonal antibodies (e.g., ipilimumab). The clinical manifestations of ipilimumab-treated subjects included general weakness, fatigue, nausea and/or mild fever and increased liver function tests such as AST, ALT, alkaline phosphatase, and/or total bilirubin. Hepatic function abnormality is defined as any increase in ALT or AST to greater than 3 × ULN and concurrent increase in total bilirubin to be greater than 2 × ULN. Concurrent findings are those that derive from a single blood draw or from separate blood draws taken within 8 days of each other. Follow-up investigations and inquiries will be initiated promptly by the investigational site to determine whether the findings are reproducible and/or whether there is objective evidence that clearly supports causation by a concurrent or pre-existing disease (e.g., cholelithiasis and bile duct obstruction with distended gallbladder) or an agent other than the investigational product. Cases where a subject shows an AST **or** ALT ≥ 3 x ULN **or** total bilirubin ≥ 2 x ULN may need to be reported as SAEs. These cases should be reported as SAEs if, after evaluation they meet the criteria for a Hy's Law case or if any of the individual liver test parameters fulfill any of the SAE criteria.

---

C O N F I D E N T I A L

- **Neurotoxicity (Neuropathy / neuromuscular toxicity)**  
Immune-mediated nervous system events include encephalitis, peripheral motor and sensory neuropathies, Guillain-Barré, and myasthenia gravis.
- **Endocrine Disorders**  
Immune-mediated endocrinopathies include hypo- and hyper-thyroidism, adrenal insufficiency, hypophysitis/hypopituitarism, and Type 1 diabetes mellitus.  
**Type 1 diabetes mellitus:** For subjects with suspected diabetes mellitus, Investigators should obtain an endocrinology consult and institute appropriate management which may include the administration of insulin.
- **Dermatitis/Rash**  
Prompt treatment with steroids (topical or systemic based on severity) is important as per current established toxicity management guidelines.
- **Nephritis and increases in serum creatinine**  

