Vaccinations should always be administered within the planned time windows given in Section 3.2. However, vaccinations may have to be delayed to allow for recovery of AEs prior to continuation of vaccine treatment. For these circumstances, maximal allowance windows have been specified below. After the delayed vaccination all subsequent vaccinations must be continued within the schedule relative to the first vaccination presented in the flow chart. If a vaccination cannot be administered within the maximal allowance windows for an administration time point, the vaccine administration for this time point has to be omitted, and further vaccinations should be given at subsequent planned time points according to the flowchart in Section 3.2.

---

CONFIDENTIAL

Maximal allowance windows due to AEs:		
Vaccination	Scheduled Week (Day 1 of)	Total extended visit window from originally scheduled vaccination (days)
2 nd	2	3
3 rd , 4 th , 5 th , 6 th , 7 th	3, 5, 7, 9, 11	7
8 th , 9 th	13, 17	10
10 th and continuing	21, 27 and every 6 weeks	28

In the event that prior to a planned blood sampling time point for immunomonitoring, the immediately preceding vaccination has to be delayed or omitted, the blood sampling has to be delayed in the same fashion to ensure that the blood sample has been obtained within 7 ± 2 days after the immediately preceding vaccination. In the event that the vaccination had to be omitted, blood sampling should occur after the next subsequent vaccine administration.

The following toxicities prohibit continuation of study treatment:

- Grade ≥ 3 study treatment-related anaphylactic reactions.
- Study treatment related AEs that are potentially life threatening or may result in permanent disability.
- Grade ≥ 3 pneumonitis/inflammatory lung disease, or other ILD
- Grade ≥ 3 study treatment-related AEs not recovering to baseline or grade 1 within 4 weeks in case of vaccination. The Sponsor should be contacted in case it is considered justifiable to continue treatment at a later time point, to approve continuation of treatment of BI 1361849, which in any case must not occur before the AE finally has resolved or recovered to baseline or grade 1.

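### Section 8.3.1 prints the permanent antibody stop for Hy's law only under Grade 3 hepatitis, so a case graded only 2 falls under a hold-and-resume rule

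*Protocol*

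**What the plan says.** Hy's law appears twice in the current protocol text and not at all in the SAP.

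- **Dosing (Protocol 8.3.1).** Under Grade 3 immune-related events, the hepatitis bullet gives three reasons for a permanent stop of both antibodies. The third is "any case meeting Hy's law criteria", by reference to an FDA guidance on drug-induced liver injury.
- **Reporting (Protocol 7.1.8).** On cases with raised transaminases or raised bilirubin it says: "These cases should be reported as SAEs if, after evaluation they meet the criteria for a Hy's Law case". This sets no dosing rule.

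Three other parts of the 8.3.1 table bear on the point:

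- A list of further permanent stops, introduced by "In addition to the criteria for permanent discontinuation of M and T depicted below", covers bullous rash, failure to taper steroids, a recurrent Grade 3 related event and biopsy-proven myocarditis. Hy's law is not in it.
- The general Grade 2 rule withholds both antibodies until the event is back to Grade 1 or below and any steroid taper has ended. It continues: "discontinue M and T permanently if such resolution does not occur within 60 days (30 days for neurotoxicities", and the bracket then closes. Hepatitis has no Grade 2 bullet of its own.
- The note at the head of the table says: "If M and T dosing is held temporarily until resolution of the event as per instructions below, treatment should resume at the next" (the sentence ends by naming the next planned dosing day).

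Section 7.1.2.3 covers hepatic function abnormality: "If no definitive underlying diagnosis for the abnormality is established, dosing of the study subject must be interrupted immediately". Each such event "will be followed by the Investigator and evaluated by the Sponsor and MedImmune/AstraZeneca".

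**The concern.** At Grade 3 the protocol treats a Hy's law case as reason to end both antibodies without waiting to see whether the liver tests recover. If a case can satisfy the criteria while each liver value stays within the Grade 2 range, the grade-specific text leads to re-exposure once the values settle. The same clinical judgement would then have opposite dosing consequences, depending on which side of a grade boundary the peak values fell. What is at stake is the safety of the individual subject on re-challenge.

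**Working it through.** **1. Can a case be only Grade 2?**

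Inputs, as multiples of ULN:

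| Limit | ALT or AST | Total bilirubin | Source |
|---|---|---|---|
| Hepatic function abnormality | > 3 | > 2, concurrent | Protocol 7.1.8 |
| Top of Grade 2 | 5 | 3 | Protocol 3.1.9, liver exceptions |

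The overlap is ALT/AST above 3 and up to 5, with bilirubin above 2 and up to 3. Examples:

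- ALT 4 and bilirubin 2.5: both 7.1.8 limits are met (4 > 3; 2.5 > 2) and neither Grade 2 ceiling is passed (4 ≤ 5; 2.5 ≤ 3).
- ALT 5.1 and bilirubin 2.5: Grade 3 or higher, because 5.1 > 5.
- ALT 4 and bilirubin 3.1: Grade 3 or higher, because 3.1 > 3.
- ALT 7 and bilirubin 4: Grade 3 or higher on both.

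The 7.1.8 limits are lower bounds, so the overlap is only the bottom corner of the range.

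**2. Does the Grade 3 item reach down to Grade 2?**

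Elsewhere the 8.3.1 table says so when a rule crosses grades. Bullous rash and biopsy-proven myocarditis are marked as applying at any grade. Endocrinopathies at Grades 3 and 4 are sent back to the Grade 2 instructions. The amylase and lipase rule is printed at both Grade 3 and Grade 4. Against that drafting, an item inside a Grade 3 bullet most naturally covers Grade 3 cases.

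**3. What does the text give at Grade 2?**

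Hold, resume at the next scheduled date once resolved, and stop permanently only if unresolved at 60 days. Classing the event as not immune-related makes no difference to the 60-day limit: the Grade 2 rule for all other adverse events also holds and uses 60 days.

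**4. How much dosing would follow?**

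Illustration: a Grade 2 case with onset on Day 30, just after the Day 29 doses.

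- Durvalumab days (Protocol 3.2): 1, 29, 57, 85, 113, 141, 169, 197, 225, 253, 281, 309, which is 12 doses.
- Tremelimumab days in Arm B: 1, 29, 57, 85, which is 4 doses, as in 6.2.3. The extra Cycle 12 mark in the 3.1.7 table is not counted.
- The 60-day limit falls on Day 30 + 60 = Day 90.
- Missed doses are taken as skipped. The stop after two consecutive missed doses in 8.3.2 is not applied, because that section covers interruptions not due to treatment-related toxicity.

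| Resolved, any taper ended | Next dose | Durvalumab still due | Tremelimumab still due |
|---|---|---|---|
| by Day 57 | Day 57 | 12 − 2 = 10 | 4 − 2 = 2 |
| Day 58 to 85 | Day 85 | 12 − 3 = 9 | 4 − 3 = 1 |
| Day 86 to 90 | Day 113 | 12 − 4 = 8 | 4 − 4 = 0 |

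These figures show what re-exposure would mean for one subject. They do not measure how often it would happen.

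**The case against.** The strongest reply is that several layers already stand between such a subject and re-dosing.

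- **Section 7.1.2.3** requires immediate interruption when no other diagnosis is found, and has the sponsor and the supplier evaluate each event. It leaves continuation to the investigator only when an unrelated cause is established. This stands, but the section gives no rule for what follows the interruption when no cause is found.
- **Section 8.4** bars continued study treatment for "Study treatment related AEs that are potentially life threatening or may result in permanent disability", with no grade limit. It also reaches the antibodies: Sections 3.1.8, 8.3 and 8.4 all say that the stricter guideline governs when the causal drug cannot be identified, which will often be so in a two- or three-drug regimen. This stands too. It still depends on someone judging a Grade 2 event potentially life threatening, and on the cause being unclear or involving the vaccine.
- **The supplier's toxicity guideline**, to which 7.1.8 and 8.3.1 refer, may settle the matter. It is not in the documents.
- **The wording** of the Grade 3 item could be read as any grade, and the Grade 2 rule is stated only in general terms. That reading is possible, but it goes against how the rest of the table is drafted.

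The reply also says, correctly, that 7.1.8 defines hepatic function abnormality rather than Hy's law, and that the documents do not say how a combined rise reported as one event is graded. Both are carried below as assumptions.

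**Conclusion.** The point holds as a defect of placement. The permanent stop for Hy's law is written at Grade 3 only, and for a case that may be only Grade 2 the grade-specific text is hold and resume. The existing safeguards reduce the risk but leave the outcome to judgement.

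This rests on two assumptions: that the 7.1.8 limits stand in for the FDA criteria, and that a combined rise is graded by its worse component on the ceilings in 3.1.9. The frequency of such cases is not given, and no trial-level effect is claimed. The matter is one to consider.

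Three stronger readings are not supported:

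- **That a Hy's law case cannot exceed Grade 2, so the stop never applies.** The limits are lower bounds and many cases will be Grade 3 or higher, where the stop works as printed.
- **That the protocol permits dosing through a Hy's law case.** No text does. Section 7.1.2.3 interrupts dosing, and the gap concerns resumption.
- **That the DLT definition in 3.1.9 is faulty and the recommended combination dose is affected.** Section 3.1.9 does not name Hy's law, but it lets a lower-grade or exempt event be declared a DLT after consultation. It also lets subjects who become non-evaluable through other toxicity be counted as DLT subjects. Leaving such an event to consultation is a design choice, and no effect on the recommended dose is shown.

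**What to change.** 1. In 8.3.1, move the Hy's law item from the Grade 3 hepatitis bullet to the list of additional permanent stops, worded to apply at any grade and whether or not the event is classed as immune-related. The last phrase is needed because that list sits under the immune-related heading.
2. In 7.1.2.3, state that after an interruption, resumption or stop follows 8.3.1 for durvalumab and tremelimumab and 8.4 for BI 1361849.
3. If dosing is finished, report whether any subject met Hy's law, at what grade, and whether the subject was dosed again. SAP 9.1.2 gives no separate presentation of events of special interest, and the shift tables in SAP 9.2 are by single parameter, so a combined rise would not show there. Cases can be found from the adverse event term for abnormal hepatic function that 7.1.2.3 prescribes, checked against the laboratory listings.

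The cost is one moved item, one sentence and a short note from data already collected. The downside is that a few Grade 2 cases would lose later antibody doses they might have tolerated.
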